## 6.3 Routine Adverse Event Reporting

All Adverse Events **must** be reported in routine study data submissions.

## 6.4 Serious or Unexpected Adverse Events Reporting

All serious (Grade 4 or 5 according to CTCAE v 4.0) or unexpected adverse events must immediately be reported to the local IRB at NorthShore University or the University of Chicago, to the data manager ([name] [contact]) and to MedWatch (fax [name]) within 7 -10 days.

## 6.5 Secondary AML/MDS

AML/MDS events must be reported. In CTCAE v 4.0, the event(s) may be reported as either: 1) Leukemia secondary to oncology chemotherapy, 2) Myelodysplastic syndrome, or 3) Treatment-related secondary malignancy.

## 7. PHARMACEUTICAL INFORMATION

A list of the adverse events and potential risks associated with the commercial agents administered in this study can be found in Sections 7.1 – 7.4.

### 7.1 Fluorouracil

#### 7.1.1 Other Names:

5-Fluorouracil, 5-FU, Adrucil, Efudex

#### 7.1.2 Classification

Antimetabolite

#### 7.1.3 Mode of Action

Fluorouracil is a pyrimidine antagonist that interferes with nucleic acid biosynthesis. The deoxyribonucleotide of the drug inhibits thymidylate synthetase, thus inhibiting the formation of thymidylic acid from deoxyuridylic acid, thus interfering with the synthesis of DNA. It also interferes with RNA synthesis. See introduction for elaboration.

#### 7.1.4 Storage and Stability

Stable for prolonged periods of time at room temperature if protected from light. Inspect for precipitate; if apparent, agitate vial vigorously or gently heat to not greater than 140°F in a water bath. Do not allow to freeze.

#### 7.1.5 Dose Specifics

Initial dose following leucovorin on day 1 of every 2 week cycle: 2400 mg/m^2 continuous infusion over 46 hours immediately following leucovorin. The 46 hour infusion should be prepared per institution guidelines.

#### 7.1.6 Administration

IV infusion.

#### 7.1.7 Incompatibilities

Incompatible with doxorubicin and other anthracyclines.

#### 7.1.8 Availability

Commercially available in 500 mg/10 mL ampules and vials, and 1 g/20 mL, 2.5 g/50 mL, and 5 g/100 mL vials. Supply for this study will be commercial.

#### 7.1.9 Side Effects

Hematologic: Leukopenia, thrombocytopenia, anemia; can be dose-limiting; less common with continuous infusion.

Dermatologic: Dermatitis, nail changes, hyperpigmentation, Hand-Foot Syndrome with protracted infusions, alopecia.

Gastrointestinal: Nausea, vomiting, anorexia; diarrhea, can be dose-limiting; mucositis, more common with 5-day infusion, occasionally dose-limiting; severe, cholera-like diarrhea which can be fatal when given with leucovorin.

Neurologic: Cerebellar syndrome (headache and cerebellar ataxia).

Cardiac: Angina, noted with continuous infusion.

Ophthalmic: Eye irritation, nasal discharge, watering of eyes, blurred vision.

Hepatic: Hepatitis with hepatic infusion.

#### 7.1.10 Nursing Implications

Monitor CBC, platelet counts.

Administer antiemetics as indicated.

Monitor for diarrhea. Encourage fluids and treat symptomatically - may be dose limiting.

Assess for stomatitis - oral care recommendations as indicated.

Monitor for neurologic symptoms (headache, ataxia).

Patients on continuous infusions may need instruction regarding central IV catheters and portable IV or IA infusion devices.

Inform patient of potential alopecia.

## 7.2 Irinotecan (CPT-11) (NSC-616348)

### 7.2.1 Other Names:

Irinotecan hydrochloride trihydrate [CPT- 11, (4S)-4, 11-diethyl-4-hydroxy-9-[(4-piperidinopiperidino) carbonyloxy] -1H-pyrido[3,4-b]indole-13,14-dione hydrochloride trihydrate] is a topoisomerase I inhibitor.

### 7.2.2 Classification

Topoisomerase I inhibitor

### 7.2.3 Toxicology

Human Toxicity: Virtually all Phase I and II studies of irinotecan have reported neutropenia and diarrhea as the dose-limiting toxicities. It is expected that these toxicities will also be encountered in this trial. Other Grade 2-3 toxicities seen include nausea and vomiting, anorexia, abdominal cramping, cumulative asthenia, thrombocytopenia, renal insufficiency, increase in transaminase level and hair loss. Sporadic cases of pulmonary toxicity, manifested as shortness of breath and nonproductive cough, have also been reported.

#### 7.2.4 Mode of Action

Causes single stranded DNA breakage by inhibition of the intranuclear enzyme topoisomerase-1. Leads to apoptotic cell death via defects in DNA repair.

#### 7.2.5 Pharmacology

7.2.5.1 Pharmacokinetics: Several studies describing the pharmacokinetic characteristics of irinotecan (CPT-11) and its active metabolite, SN-38, when administered alone or in combination with other agents (including cisplatin) in patients with small cell or non-small cell lung cancer have been reported in published literature. CPT-11 is converted by carboxylesterases to its more active metabolite, SN-38. In vitro, SN-38 is 250 to 1,000 fold more potent than CPT-11 in the inhibition of topoisomerase I activity. A reversible, pH-dependent hydrolysis converts the closed lactone E ring form of both CPT-11 and SN-38 to the open, carboxylate form of each compound. Only the closed ring (lactone) forms of CPT-11 and SN-38 are effective topoisomerase I inhibitors. The mean terminal half-life of SN-38 in plasma is slightly longer than that for CPT-11;  $11.5 \pm 3.8$  hours versus  $6.3 \pm 2.2$  hours for the lactone forms. Peak plasma concentrations for CPT-11 occur at the end of the infusion. The time to peak for SN-38 is highly inter-patient dependent occurring at variable times points 30 to 90 minutes after the end of infusion. Murine studies suggest that the liver may concentrate, convert CPT-11 to SN-38, and eliminate both compounds as well as the glucuronide conjugate of SN-38 (SN-38G) via biliary secretion. In rats, 55% of radiolabeled CPT-11 was excreted unchanged in the bile within 24 hours, while 21.7% was transformed to SN-38. It recently was demonstrated that plasma concentrations of SN-38G in patients occur 0.5 to 3 hr after the SN38 peak and plasma levels generally exceeded that of SN-38. Overall, 73% of the radioactivity could be recovered from the feces of rats and 25% from the urine. Bile concentrations of CPT-11 were 10 to 60 fold higher than plasma concentrations in one patient during the first 6 hours following administration, while bile concentrations of SN-38 were 2 to 9 fold higher. Renal clearance has not been reported to be a major route of elimination for these compounds in humans.

#### 7.2.6 Formulation

The drug is supplied in two forms: 2 ml vials containing 40 mg of drug and 5 ml vials containing 100 mg of drug. The drug is supplied in brown vials and appears as a pale-yellow-to-yellow crystalline powder and pale yellow transparent solution when reconstituted.

#### 7.2.7 Storage and Stability

Irinotecan vials must be stored in a cool, dry place, protected from light in a locked cabinet accessible only to authorized individuals. It is stable for at least three years at room temperature. Irinotecan is stable for 24 hours in glass bottles or plastic bags after reconstitution with D5W.

#### 7.2.8 Dose Specifics

Irinotecan will be given at a dose of 180 mg/m^2 intravenously over 90-120 minutes every 2 weeks.

### 7.2.9 Preparation

Irinotecan will be diluted with D5W to a total volume of 500 ml and infused intravenously over 90-120 minutes. Nothing else should be added to the bag.

### 7.2.10 Route of Administration

Intravenous administration only.

### 7.2.11 Incompatibilities

Do not mix with any other compound.

### 7.2.12 Availability

This drug is commercially available for purchase by a third party. This drug will not be supplied by the NCI.

### 7.2.13 Side Effects

Hematologic: Leukopenia, neutropenia, anemia, thrombocytopenia, neutropenic fever, hemorrhage

Gastrointestinal: Diarrhea (early and late – see administration above), nausea and vomiting, anorexia, abdominal pain, flatulence, stomatitis, dyspepsia, dehydration

Hepatic: Elevated transaminases.

Cardiovascular: Vasodilation, hypotension, myocardial infarction, stroke, edema

CNS: Dizziness, confusion, somnolence, insomnia, back pain

Respiratory: Pulmonary embolism,

Dermatologic: Alopecia, rash

Other: Asthenia, thrombophlebitis, sweating, weight loss, chills

### 7.2.14 Nursing/Patient Implications

Premedicate with antiemetics in anticipation of mild to moderate nausea and vomiting. When used in combination with 5-fluorouracil and leucovorin the nausea and vomiting will likely be worse.

Fatalities have been reported with thromboembolic events and neutropenic sepsis in patients receiving 5-fluorouracil, leucovorin and irinotecan.

Monitor for diarrhea. Diarrhea occurring within one hour of irinotecan has been treated with atropine 0.25 to 1mg IV or SC. Loperamide has been effective in treating later diarrhea and the patient should be instructed on its immediate use at the first loose stool following the irinotecan (see section 5.5.2).

Monitor CBC, platelets, and liver function tests.

Dose modifications per the protocol should be followed for hematologic and gastrointestinal toxicity.

Advise patient of likely post-treatment neutropenia and instruct in appropriate neutropenic precautions.

Administration of an oral quinolone antibiotic may decrease the risk of neutropenic sepsis in patients receiving 5-fluorouracil/leucovorin and irinotecan

## 7.3 Oxaliplatin

### 7.3.1 Generic Name

Oxaliplatin

### 7.3.2 Other name

L-OHP

### 7.3.3 Classification:

Platinating agent

### 7.3.4 Mode of Action

Oxaliplatin has properties similar to those of a bifunctional platinating agent, producing DNA cross-links and other damage to DNA.

### 7.3.5 Storage and Stability

Oxaliplatin should be stored at controlled room temperatures between 20° to 25°C in the light-proof packaging provided.

Oxaliplatin injection: Store between 20°C and 25°C (68°F to 77°F) with excursion permissible between 15°C and 30°C (59°F to 86°F). Do not freeze. For long-term storage, protect product from light (keep vial in outer carton). Stable for 3 years under these conditions.

#### Diluted Solutions

After dilution in 250-500 mL of 5% Dextrose in Water, diluted solutions are stable for 6 hours at room temperature (20°C to 25°C; 68°F to 77°F) or up to 24 hours under refrigeration (2°C to 8°C; 36°F to 46°F).

### 7.3.6 Dose Specifics

85 mg/m^2 intravenously over 2 hours every 2 weeks, for 4 cycles both pre- and postoperatively.

### 7.3.7 Preparation

Oxaliplatin injection: Withdraw the calculated dose of the 5 mg/mL solution from the vial(s) and then dilute with 250 mL to 500 mL Dextrose 5% in Water to give an oxaliplatin concentration between 0.2 mg/mL and 2.0 mg/mL. **Do not reconstitute or dilute oxaliplatin with a sodium chloride solution.**

**Do not use administration needles or intravenous infusion sets containing aluminum items (risk of degradation of oxaliplatin upon contact with aluminum) for the preparation or administration of either the oxaliplatin for injection or the oxaliplatin injection.**

### 7.3.8 Route of Administration

Intravenous.

### 7.3.9 Incompatibilities

Do not combine with alkaline medications or media (such as basic solutions of 5-FU, trometamol) which cause oxaliplatin to degrade. Do not use needles or IV infusion sets containing aluminum items for the preparation or administration (risk of degradation of oxaliplatin on contact with aluminum). Since little or no compatibility data exist on oxaliplatin at present, it should not be mixed or combined with anything

other than 5% dextrose injection USP. The reconstitution or final dilution must never be performed with a sodium chloride solution.

#### 7.3.10 Availability

For this clinical trial, the supply of oxaliplatin will be commercial.

**Oxaliplatin should be discontinued for any suspected occurrence of hemolytic uremic syndrome.**

**Constitutional Symptoms:** Fever (in the absence of neutropenia, where neutropenia is defined as AGC < 1.0 x 10^9L), fatigue (lethargy, malaise, asthenia), rigors/chills,

insomnia, sweating, weight gain, weight loss.

Dermatology/Skin: Erythema or skin eruptions, alopecia, hand-foot skin reaction, injection site reaction, rash/desquamation, urticaria, pruritus/itching, dry skin, nail changes, pigmentation changes.

Endocrine: Hot flashes/flushes.

Gastrointestinal: Anorexia, ascites (non-malignant), colitis, constipation, dehydration, diarrhea, dysphagia, enteritis, esophagitis, flatulence, gastritis, gastrointestinal reflux (heartburn, dyspepsia), ileus (or neuroconstipation), intestinal obstruction, nausea, odynophagia (painful swallowing), stomatitis /pharyngitis (oral/pharyngeal mucositis), taste disturbance (dysgeusia), typhilitis, ulcer, vomiting, xerostomia (dry mouth).

Hemorrhage: CNS hemorrhage/bleeding, hemoptysis, hemorrhage/bleeding with grade 3 or 4 thrombocytopenia, melena, GI bleeding, rectal bleeding/hematochezia, pulmonary hemorrhage, vaginal hemorrhage, other (hemorrhage NOS).

Hepatobiliary/Pancreas: increased alkaline phosphatase, increased bilirubin, increased GGT (gamma glutamyl transpeptidase), hepatic enlargement, increased SGOT (AST) (serum glutamic oxaloacetic transaminase), increased SGPT (ALT) (serum glutamic pyruvic transaminase), pancreatitis, hepatic veno-occlusive disease (manifested by hepatomegaly, ascites, and jaundice).

Infection/Febrile Neutropenia: Febrile neutropenia (fever of unknown origin without clinically or microbiologically documented fever (ANC <1.0 x 10^9/L fever >38.5°C), infection (documented clinically or microbiologically with grade 3 or 4 neutropenia (ANC <1.0 x 10^9/L), infection with unknown ANC, infection without neutropenia.

Metabolic/Laboratory: Acidosis (metabolic or respiratory), hypoalbuminemia, hypocalcemia, hyperuricemia, hyperglycemia, hypoglycemia, hypokalemia, hypophosphatemia, hyponatremia, hypomagnesemia

Musculoskeletal: Involuntary muscle contractions, trismus.

Neurology: Ataxia (incoordination, including abnormal gait), cerebrovascular ischemia, confusion, dizziness, extrapyramidal movements/restlessness, insomnia, mood alteration (depression, anxiety), neuropathy cranial (ptosis), vertigo, acute sensory neuropathy induced or exacerbated by cold (including acute laryngopharyngeal

dysesthesias, Lhermitte's sign, upper extremity paresthesia), chronic peripheral neuropathy (paresthesias, dyesthesias, hypoesthesias), seizure, somnolence, speech impairment, syncope.

Ocular/Visual: Conjunctivitis, vision abnormalities including blindness, optic neuritis, papilledema, hemianopsia, visual field defect, transient blindness.

Pain: abdominal pain or cramping, athralgia (joint pain), bone pain, chest pain (noncardiac and non- pleuritic), headache (including migraine), myalgia (muscle pain including cramps and leg cramps).

Pulmonary/Upper Respiratory: Bronchospasm/wheezing, Pulmonary fibrosis, cough, dyspnea (shortness of breath), hiccoughs (hiccups, singultus), pneumonitis/pulmonary infiltrates (including eosinophilic pneumonia, interstitial pneumonitis, and interstitial lung disease), laryngospasm, nasal cavity/paranasal sinus reactions, voice changes (hoarseness, loss or alteration in voice, laryngitis).

Renal/Genitourinary: Increased creatinine, renal failure, urinary retention, urinary urgency, dysuria. Hemolytic Uremic Syndrome (HUS) – see coagulation.

Vascular: Phlebitis, thrombosis

Also reported on oxaliplatin trials but with the relationship to oxaliplatin still undetermined: tongue paralysis, anemia, aphasia, abnormal hepatic function, hyporeflexia, anxiety, depression, dysarthria, insomnia, increased sweating, rhinitis, epistaxis, gout, pancreatitis, idiopathic thrombocytopenia (5 cases), thrombocytopenia associated with hemolytic anemia (2 cases).

**NOTE:** Oxaliplatin in combination with other agents could cause an exacerbation of any adverse event currently known to be caused by the other agent, or the combination may result in events never previously associated with either agent.

### 7.3.12 Nursing Implications

Monitor CBC, platelet counts.

Administer antiemetics as indicated.

Monitor for diarrhea. Encourage fluids and treat symptomatically.

Monitor for neurological symptoms (paresthesias, dysesthesias, etc.).

Instruct patient on the care of access devices.

Inform patient of expected side effects.

Respiratory problems (i.e., pulmonary fibrosis, cough, dyspnea, rales, pulmonary infiltrates, hypoxia, and tachypnea) have been observed in patients administered with oxaliplatin. In rare cases, death has occurred due to pulmonary fibrosis. Please monitor and instruct the patient to report any respiratory difficulties and hold oxaliplatin until interstitial lung disease is ruled out for cases of grade >3.

All patients must be premedicated for nausea and vomiting (see below).

Patients on this study should be counseled to avoid cold drinks and exposure to cold water or air because the neurotoxicity often seen with oxaliplatin appears to be exacerbated by exposure to cold. The period of time during which the patient is at risk for these cold-induced sensory neuropathies is not well documented. Patients should exercise caution regarding cold exposure during the treatment period.

Peripheral sensory neuropathies can occur at any time after receiving oxaliplatin therapy. There have been deaths reported, especially in the elderly, while receiving Oxaliplatin/5-FU 130 mg/m^2, 5-FU 320 mg/m^2, Leucovorin 20 mg day 1-5 every three weeks. Patients had hypotension, weakness and diarrhea. They were not all neutropenic. These were thought to result from diarrhea complicated by enteric sepsis with dehydration and hypotension. Any patient with fever, grade 3 diarrhea, or grade 4 neutropenia/ANC with or without fever should be monitored closely, and hospitalization should be considered for fever, appropriate hydration, intravenous antibiotic therapy appropriate for gram positive and negative sepsis, and support for clinically significant deterioration. Patients should be supported aggressively until neutropenia and fever resolve.

Among over 50,000 patients that have been treated with Oxaliplatin, 11 patients developed respiratory problems. Four deaths occurred in these 11 patients, 2 of which were due to pulmonary fibrosis. As the relationship of such toxicity to Oxaliplatin cannot be confirmed, patients must be monitored closely for unexplained respiratory problems (i.e., pulmonary fibrosis, cough, dyspnea, rales, pulmonary infiltrates, hypoxia, and tachypnea) and Oxaliplatin must be held until interstitial lung disease is ruled out for cases of grade > 3.

Antiemetic premedications will be given as used for any platinum-containing regimen. The antiemetic regimen will be defined by the participating institution.

Antiemetic agents for platinum-induced nausea and vomiting are also effective for the prevention and treatment of oxaliplatin-induced nausea and vomiting.

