## 4.3 Data and Safety Monitoring Plan

Data Safety and Monitoring will occur monthly at NorthShore University protocol review meetings, which are led by senior level medical oncologists. At each meeting, all active studies are reviewed for safety and progress toward completion. Toxicities and adverse events will be reviewed at each meeting and a Data Safety and Monitoring form will be filled out for this protocol and signed by either the chairperson or by his/her designee if he/she is not available. Biweekly telephone calls will take place between the principal investigators at NorthShore University and University of Chicago to review all toxicity and adverse event data. *Please see Appendix B for full details.*

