### 5.3.6 Other toxicities

Any other toxicity  $\geq$  grade 2, except anemia and alopecia, may require a reduction in the dose of irinotecan to 150 mg/m^2 and/or oxaliplatin to 60mg/m^2 and/or 5FU of 25% depending on the type of adverse event.

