## 5.4 Duration of Therapy

5.4.1 Including treatment delays due to adverse event(s), as specified in section 5.3, *initial preoperative* chemotherapy treatment with FOLFIRINOX will continue for 4 cycles or until one of the following criteria applies:

- Disease progression,
- Intercurrent illness that prevents further administration of treatment,
- Unacceptable adverse event(s),
- Patient decides to withdraw from the study, or
- General or specific changes in the patient's condition render the patient unacceptable for further treatment in the judgment of the investigator.

5.4.2 Following successful surgery, subsequent FOLFIRINOX will be given for 4 cycles or until one of the aforementioned criteria for stopping applies.

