### 5.6 Criteria for Removal from Study

*Patients will be removed from study when any of the criteria listed in Section 5.4 applies. The reason for study removal and the date the patient was removed must be documented in the Case Report Form.*

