## 8. STUDY CALENDAR

**Schedules shown in the Study Calendar below are provided as an example and should be modified as appropriate.**

Baseline history, physical and blood work are to be conducted within 2 weeks prior to start of protocol therapy. Scans and x-rays must be done  $\leq 4$  weeks prior to the start of therapy. Laboratory evaluations should be repeated within 24 hours prior to initiation of the next cycle of therapy. [ Cycle 1 refers to week of first actual therapy with mFOLFIRINOX.]

	Pre-Study	Cycle 1	Cycle 2	Cycle 3	Cycle 4	Week +4 weeks after Cycle 4 completion	Week +4-6 After Cycle 4 completion	Cycle 5 e	Cycle 6	Cycle 7	Cycle 8	Week +4 after completion of Cycle 8	Off Study d
Informed consent	X												
Demographics	X												
Medical history	X		X	X	X	X		X	X	X	X	X	X
Toxicity Assessment			X	X	X	X			X	X	X	X	
Physical exam	X		X	X	X	X		X	X	X	X	X	X
Vital signs	X	X	X	X	X	X		X	X	X	X	X	X
Height	X												
Weight	X	X	X	X	X	X		X	X	X	X	X	X
Performance status	X	X	X	X	X	X		X	X	X	X	X	X
CBC w/diff, plts	X		X	X	X	X		X	X	X	X	X	X
Serum chemistry a	X		X	X	X	X		X	X	X	X	X	X
Pregnancy test b	X							X					
CA 19-9	X			X		X		X		X		X	X
Radiologic evaluation c	X					X		X				X	
Chemotherapy		X	X	X	X			X	X	X	X		
Surgery							Exact timing per surgeon						

- a. Specific minimal lab tests required –Na, K, Mg, Phosphorus, Glucose, BUN,CO2, Chloride Creatinine, Calcium, Total Protein, Albumin, Total Bilirubin, Alkaline Phosphatase, SGOT, SGPT      b. May be serum or urine.
- c. CT scan of chest/abdomen/pelvis **or** MRI of abdomen/pelvis plus CXR if CT scan cannot be done.
- d. Follow up visits and studies per usual standard of care but not less than every 3 months for years 1-2 and every 6 months for years 3-5.
- e. Cycle 5 starts 4-10 weeks after surgery depending on patient recovery

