## 11.4 **Plans for analysis including plans for formal interim analysis.**

The proportion of patients completing preoperative therapy and undergoing resection will be calculated, and a confidence interval constructed based on the binomial distribution. Progression-free and overall survival will be calculated by using the method of Kaplan and Meier. The frequency of various AEs (worst grade) will be tabulated.

Because surgery-related deaths are of concern after administration of FOLFIRINOX, there will be close monitoring of this adverse event. Specifically, a stopping rule developed by Goldman will be used as a guide for early termination due to surgery-related deaths. The trial may be halted if there is evidence that the true mortality rate is increased from an acceptable level of 3% to an upper limit of 10% assuming an alpha level of 5% and power of 80%. The stopping rule requires that early termination be considered if 3 deaths occur in the first 14 or fewer patients or four deaths in the first 31 or fewer patients. Additionally, febrile neutropenia, platelet counts less than 20,000, and diarrhea requiring hospitalization are also of concern. A stopping rule, based on an acceptable level of 10% and upper limit of 20%, requires that early termination be considered if 4 such adverse events occur in the first 4 patients, 5 such adverse events occur in the first 10 or fewer patients, 6 such adverse events in the first 17 or fewer patients, or 7 such adverse events in the first 24 or fewer patients. Delayed time to surgery and delayed wound healing are also of concern and will be reported and tabulated carefully. In order to monitor these events very closely, there will be a weekly telephone call between site PI's, and any events of concern will be immediately disseminated for discussion by all investigators. A monthly report will be generated for distribution to all investigators to update the group on the status of the study and of the patients on the study. Any concerns will receive immediate attention by the PI's.

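### As printed, the oxaliplatin hold to rule out interstitial lung disease starts only above grade 3, leaving redosing after a grade 3 event to judgment

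*Combined protocol and SAP*

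**What the plan says.** Section 7.3.12 (oxaliplatin, Nursing Implications) gives the rule in two places. One paragraph asks staff to monitor respiratory symptoms and "hold oxaliplatin until interstitial lung disease is ruled out for cases of grade >3". A later paragraph, after reporting the historical respiratory cases, makes it an obligation: "Oxaliplatin must be held until interstitial lung disease is ruled out for cases of grade > 3". The symptoms named in both include cough, dyspnea, rales, infiltrates and hypoxia. The later paragraph also requires close monitoring for unexplained respiratory problems, with no grade attached.

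The dose-modification rules in section 5.3 have no entry for lung toxicity. The catch-all in 5.3.6 covers any other toxicity of grade 2 or more, "except anemia and alopecia, may require a reduction in the dose of irinotecan", and it extends to oxaliplatin and 5FU. Section 5.4.1 ends preoperative treatment for unacceptable adverse events, or when changes in the patient's condition make the patient "unacceptable for further treatment in the judgment of the investigator". Section 5.4.2 carries these criteria into the postoperative cycles. Section 5.6 then makes removal compulsory: "Patients will be removed from study when any of the criteria listed in Section 5.4 applies".

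**The concern.** The hold exists so that a patient with unexplained respiratory toxicity does not receive more oxaliplatin before interstitial lung disease has been excluded. A strict sign puts grade 3 outside the compulsory rule. A patient with grade 3 dyspnea or infiltrates could then be redosed before the lung work-up if the investigator so judged, and that would not be a protocol deviation.

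The stake is the safety of individual patients, not inference. Section 7.3.12 reports 4 deaths among 11 patients with respiratory problems, 2 of them from pulmonary fibrosis, and adds that a causal link to oxaliplatin could not be confirmed. The authors thought the risk serious enough to state the hold twice, so the grade at which it starts should be the intended one.

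**Working it through.** **1. What the sign means.** Sections 5.3 and 6.2 specify version 4 of the NCI criteria, and the protocol uses whole grades up to 5 (section 6.4 refers to grades 4 and 5).
- Strictly above 3: grades 4 and 5.
- 3 or above: grades 3, 4 and 5.
- The only difference is grade 3.

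**2. Does any other rule require a hold at grade 3?**
- 5.3.1 to 5.3.5 and 5.3.7: no pulmonary entry.
- 5.3.6: an optional reduction. It is not a hold and asks for no lung work-up.
- 5.3 (opening and closing text): off study only if the same grade 4 toxicity recurs after a dose reduction.
- 5.4.1 with 5.6: removal is compulsory, but only once the event is judged unacceptable or the patient unfit. No grade is set.
- Section 8: toxicity assessment at cycles 2-4, cycles 6-8 and both visits 4 weeks after a chemotherapy phase; vital signs at every cycle; physical examination at cycles 2-8. Chest imaging is due at baseline, 4 weeks after cycle 4, at cycle 5 and 4 weeks after cycle 8, by CT or by "MRI of abdomen/pelvis plus CXR if CT scan cannot be done". These help to find an event; none withholds a dose.
- 4.3: monthly safety review, and calls between the principal investigators "to review all toxicity and adverse event data". 11.4: "any events of concern will be immediately disseminated for discussion by all investigators". These communicate events; they do not require a hold.

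No passage found requires oxaliplatin to be withheld at grade 3 pending exclusion of lung disease.

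**3. Comparison with the protocol's other thresholds.**

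| Toxicity | Section | Action applies at |
|---|---|---|
| Thrombocytopenia between cycles | 5.3.1b | grade 3-4 |
| Diarrhea | 5.3.2 | grade 3-4 |
| Mucositis, hand-foot syndrome | 5.3.3 | grade 3-4 |
| Neuropathy | 5.3.7 | grade 3 at any duration; grade 2 if persistent |
| Suspected hemolytic uremic syndrome | 7.3.11, 7.3.12 | no grade: hold or discontinue |
| Possible interstitial lung disease | 7.3.12 | above grade 3 |

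Neutropenia without fever or infection is the exception in 5.3.1b: it needs grade 4 for more than 7 days before a reduction. Even there, 5.3.1a blocks the next cycle until granulocytes reach 1.5 x 10^9/L. The protocol gives no reason for a higher threshold for the lung.

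**4. Size.** The plan states no expected number of cases. The only input is the count in 7.3.12, 11 patients in over 50,000 (any grade), applied to the planned maximum of 21 patients (11.3).
- Rate: 11 / 50,000 = 2.2 per 10,000.
- Expected cases: 21 x 11 / 50,000 = 0.0046.
- Chance of at least one: 1 - (1 - 11/50,000)^21 = 0.46%.
- Exact 95% Poisson limits for a count of 11 are 5.49 and 19.68. Then 21 x 5.49 / 50,000 = 0.0023 and 21 x 19.68 / 50,000 = 0.0083 expected cases, or a 0.23% to 0.82% chance of at least one.

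These limits reflect only sampling error in the historical count. They do not bound how often the rule would be triggered here. The rule is triggered by symptoms, including cough and dyspnea. Section 6.1.1 lists persistent cough, dyspnea and pulmonary fibrosis among the common, expected events of oxaliplatin, and dyspnea for irinotecan. The documents give no rate of grade 3 respiratory symptoms, so the trigger frequency is unknown.

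**The case against.** The strongest objection is that the sign may not be what the authors wrote. The text examined was extracted from the PDF, and an underlined greater-than sign, meaning greater than or equal, could have been read as a plain one. The greater-than-or-equal symbol survives elsewhere, for example in 5.3.5 and 5.3.6, but it appears nowhere in section 7 as read. Its survival also says little about an underlined sign in running text, since underlining is preserved only inside the tables of 5.3. The two sentences do not corroborate each other, because the same loss would affect both. This objection stands, and it is why the source page must be checked before anything is changed.

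A second objection is that the two sentences agree with each other and no passage says grade 3 was intended, so the threshold may be the sponsor's choice. That is partly right: there is no internal contradiction. But the grade 3 alternative comes from the protocol's own pattern in step 3, not from outside preference.

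A third objection is that grade 3 is already managed. This is true as far as it goes. A reader might infer that a grade 3 lung event goes unmonitored, or that redosing is required. Neither follows: patients are assessed before nearly every dose, reduction and stopping are available, and nothing forbids a hold. What is missing is only the obligation to hold.

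**Conclusion.** The point holds for the text as printed: the compulsory hold starts at grade 4, and at grade 3 redosing before lung disease is excluded is left to judgment. It rests on two assumptions: that the source page really prints a strict sign, and that no redacted or removed text supplies a hold at grade 3. If the source page prints greater than or equal to 3, the point falls away.

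The size is small on the historical count, about 0.005 expected cases in 21 patients, but the frequency of the trigger itself is unknown. A reader might take 0.46%, or the upper figure of 0.82%, as a ceiling. The documents do not support that, for the reason given in step 4. A reader might also infer that the two-stage decision or the stopping rules are affected. No effect on the primary endpoint is claimed, and neither stopping rule in 11.4 refers to lung toxicity. This is a low-priority safety correction, held with low-to-medium confidence.

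**What to change.** Check the sign on the source page of 7.3.12. If it is strict, write grade 3 or higher in both sentences. If it already reads greater than or equal to 3, leave it. A one-line pointer from section 5.3 to this hold would be useful but is optional, since prescribers will look there for dose rules.

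The cost is a short wording change in two sentences, with no added data, visits or patients. The only clinical downside is an occasional extra delay to a cycle while lung disease is excluded in a patient with grade 3 symptoms.
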